**b. Data**

The study features a series of questionnaires in the initial visit, and a combination of questionnaires alternating with desktop behavioral tests during the second visit. Below are the descriptions of each measure:

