**1. Purpose and Objectives:**

This protocol does not include any administration of medication or other interventions. This protocol will record cognitive performance and decision-making behavior in Veterans who seek mental health services in the substance use disorder intensive outpatient program (IOP). The goal is to identify the neurobehavioral effects of a structured, brief cognitive-based psychotherapy currently being conducted in the IOP along with other supportive, unstructured, treatments. The benefit of this study will be to obtain a better understanding of neurobehavioral changes occurring from evidence-informed treatments.

Aim 1: To determine if measurable neurobehavioral function in the domains of problem solving, decision making, and motoric impulsivity is predictive of treatment success and adherence outcomes (e.g. Urinary Drug Screen/Breathalyzer Analysis results, appointment no shows, early drop out, recidivism).

Exploratory Aim: To determine if there are between group differences in neurobehavioral function as a result of treatment modality being received as standard of care in the substance use outpatient setting.

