**2. Background, Significance, and Scientific Rationale:**

It is established that impulsivity is a tremendous risk factor for the development of addiction (Bickel et al., 2007) and for treatment failure (Loree, Lundahl, & Ledgerwood, 2015). Impulsivity is a multi-faceted trait that has been conceptually divided into a more decision-based domain and rapid “acting without thinking” motoric domain(Swann, [name], Moeller, & Dougherty, 2002), where greater impulsivity in both domains has been found in patients addicted to stimulants in particular (Ahn & Vassileva, 2016). Trait personality measures of impulsivity typically capture some elements of both domains and frequently correlate poorly with individual task metrics of impulsivity. Therefore, comprehensive assessment of cognitive change (as it may underlie improvements in mental perseverance and thus changes in substance use) should include objective behavioral measures of both decision-making and motoric impulsivity. The addition of focused neurocognitive tasks holds potential to *identify mechanisms of* psychotherapy effects, such as whether a structured cognitive behavioral therapy may reduce substance use by promoting mindful attention generally, or whether it influences future-orientation specifically.

There are currently multiple treatments being conducted in the IOP clinic as standard of care, with a particular psychotherapy of interest for this study being a brief, structured cognitive-based treatment, called the Mind Freedom Plan (MFP). This treatment is one of two treatments being administered, with the other being a supportive, unstructured treatment that is also provided as standard of care. The aim of the MFP treatment is to improve problem solving abilities, increase engagement in pleasurable activities, and teach the patient to identify and change maladaptive thoughts. Structured worksheets for each session have been developed for

the purpose of achieving these goals. An exploratory aim of the current study will be to identify whether there are neurobehavioral differences in subjects as a result of the treatment modality being conducted during their treatment regimen. This is novel due to the lack of studies previously examining neurobehavioral impulsivity tasks as a metric for exploring differences in treatment modality.

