The VA has an increasing need for brief, efficacious interventions to assist Veterans in reducing alcohol and substance abuse. The emphasis on brief therapies is partly due to VA initiatives and ongoing access concerns that have limited the number of sessions providers are allotted with patients. Additionally, there are significant efforts to roll out and integrate evidence based practices across the VA. This exploratory aim will be an effort to meet the intersection of these demands by examining a brief evidence-informed therapy for substance users in outpatient treatment. The focus of this aim will be to determine whether this treatment results in measurable changes in neurobehavioral performance shown to be aberrant in addiction. These behaviors might serve as *early-indicator proxy markers* for improvement in cognitive domains relevant to addiction, which could in turn result in longer-term benefits of alcohol or drug abstinence.

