### **3. Study Design:**

This protocol will recruit approximately 35 Veterans once they enroll in the McGuire VA Medical Center Substance Abuse Treatment Program (SATP) IOP to complete two sessions of questionnaires and neurobehavioral measures, lasting approximately 3 hours in total. Each subject will meet initially with research staff after their SATP intake (conducted as standard of care), but prior to initiating treatment for the first session. Subjects will then meet with research staff again approximately one month later following their completion (or potentially incompletion) of the treatment. Following this meeting, research staff will complete a targeted CPRS medical chart review to collect information on appointment no shows, early termination of services, and results of Urinary Drug Screen (UDS) and Breathalyzer collections, and results of the Beck Depression Scale and Quality of Life Inventory administered during the SATP intake. 90 days following this chart review, a second chart review will occur to collect the same information, if available, for the post-treatment time period, along with information about whether they have re-entered treatment.

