### **4. Methods:**

#### **a. Procedures:**

The study will take place at the Substance Abuse Rehabilitation Program-Intensive Outpatient Program (IOP) of the Richmond VA Medical Center (RICVAMC). To minimize subject burden, consent and the first visit testing procedures will take place in the same visit to RICVAMC if possible. The study entails two visits with study staff. The first visit will include retrieving informed consent, and once enrolled, the completion of several questionnaires (see below). This visit is expected to last 60-90 minutes. The subject will then be scheduled for a follow up visit in to be conducted after he/she completes the intensive outpatient substance use program. This visit will last approximately 2 hours, and will involve questionnaires and desktop performance based tasks (see below)

**CPRS Chart Review.** CPRS records will first be reviewed by research study staff (research assistants) for intake and progress notes pertaining to the entry into IOP. When a Veteran is

identified to be entering the program and is determined to not have legal involvement from examining the intake, the Veteran will be contacted by research staff in a face-to-face encounter in the SATP clinic to explore his/her interest in participating in the current study. If interested, an appointment will be scheduled to meet to complete informed consent and the initial self-report tests. For the purposes of this study, legal involvement will be defined as a current legal issue identified during the clinic screening that mandates the completion of a substance use treatment program.

Once a subject has consented and is confirmed eligible to participate in the protocol, he or she will be assigned a five-digit ID number for this protocol. The subject will be identified by this number on all study forms, questionnaires, and surveys. The file that links a subject's name and other personally-identifiable information to this ID code number will be an electronic excel file on a password-protected virtual drive furnished by VA.

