CPRS will also be used to complete a review following the second visit with subjects to collect information on appointment no shows, early termination of services, results of Urinary Drug Screen (UDS) and Breathalyzer collections, and results of the Beck Depression Inventory and Quality of Life Inventory administered during the SATP intake. 90 days following this chart review, a second chart review will occur to collect the same information, if available, for the post-treatment time period, along with information about whether they have re-entered treatment.

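### Aim 1 calls the behavioral tasks predictive, but they are first given after treatment, so for the Day 0–28 outcomes they support only a retrospective association

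*Protocol*

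**What the plan says.** Aim 1 (Section 1) asks whether function in problem solving, decision making and "motoric impulsivity is predictive of treatment success and adherence outcomes". The outcomes it names are drug and breath test results, missed appointments, early drop-out and recidivism. The second aim is labelled exploratory.

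Section 4b describes "a series of questionnaires in the initial visit, and a combination of questionnaires alternating with desktop behavioral tests during the second visit". The Tower Test, delay discounting, stop-signal and emotional Go-NoGo tasks all stand under Visit Two. Visit One holds four self-report scales: BAM, BIS-11, PTSD checklist and Beck Anxiety Inventory. The timeline table puts baseline at Day -7 to -1, treatment at Day 0–28, the three computer tasks and the first chart review at Day 29–35, and the last chart review at Day 120. Of that last review, Section 4a says that "a second chart review will occur to collect the same information, if available, for the post-treatment time period"; treatment re-entry is added to it.

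Section 2 gives as a purpose to "determine whether this treatment results in measurable changes in neurobehavioral performance shown to be aberrant in addiction", meaning MFP.

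On who attends Visit 2, Section 3 places it "approximately one month later following their completion (or potentially incompletion) of the treatment", while Section 4a has it "to be conducted after he/she completes the intensive outpatient substance use program".

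**The concern.** A predictor has to be measured before the outcome it predicts. For no-shows, early drop-out and in-program drug tests the order is reversed, and what happens in between is a treatment that the protocol expects may move the scores. Someone who drops out receives less of it. If drop-outs then score worse at Visit 2, the cause may be impulsivity that was there at intake, or less treatment. The planned data cannot tell these apart.

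The conclusion of the main aim is at stake: a report that task performance predicts adherence during the program would claim something the schedule cannot show. A pre-treatment task score also cannot be recovered once a participant has started treatment.

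**Working it through.** **Order of dates** (timeline table; Sections 3, 4a and 4b)

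| Item | When | Before or after the tasks |
|---|---|---|
| BAM, BIS-11, PTSD checklist, Beck Anxiety Inventory | Day -7 to -1 | before |
| No-shows, early drop-out, in-program drug and breath tests | Day 0–28 | before |
| Four behavioral tasks (Visit 2) | Day 29–35 | – |
| Re-entry, post-treatment drug and breath tests | up to second review | after |

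An in-program event precedes the tasks by at least 29 − 28 = 1 day and at most 35 − 0 = 35 days. The second review falls at 29 + 90 = 119 to 35 + 90 = 125, which agrees with the stated Day 120. Only the last row can be predicted from task scores. The table does not list the Tower Test; its Visit 2 placement comes from Section 4b.

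**Direction of the analysis.** Data Analysis lists the task scores (delay-discounting constant, stop-signal reaction time, Go-NoGo reaction time, Tower Test errors) as dependent variables. No analysis stated there uses a task score as a predictor of a later outcome.

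**Illustrative size.** The protocol gives no drop-out rate, amount of treatment received by drop-outs, or effect on the tasks, so all of these are assumed.

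- n = 35 (Section 3), everyone tested, no true prediction.
- Drop-out 30%. Fraction of treatment received: 1 for completers, uniform on 0 to 0.5 for drop-outs (mean 0.25).
- Score = standard normal − δ × fraction × M, where M = 1 for MFP participants and 0 otherwise, independent of drop-out.
- MFP share one half, or two thirds if each of the three providers in Section 7 is equally likely.
- Pooled t-test of completers against drop-outs at 5%, 100,000 replicates per setting.

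Mean spurious difference = δ × (1 − 0.25) × MFP share. At δ = 0.5 SD:

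- half MFP: 0.5 × 0.75 × 0.5 = 0.19 SD
- two-thirds MFP: 0.5 × 0.75 × 2/3 = 0.25 SD

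False rejection rate at 30% drop-out:

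| δ (SD) | half MFP | two-thirds MFP |
|---|---|---|
| 0 | 5.0% | 5.0% |
| 0.2 | 5.5% | 5.7% |
| 0.5 | 7.4% | 9.5% |
| 0.8 | 10.9% | 16.0% |

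With drop-out from 20% to 40%, the 0.5 SD rates run 6.4–8.0% (half) and 8.3–10.3% (two-thirds). The completer versus drop-out test is inferred from the task hypotheses about adherence; Data Analysis does not spell it out.

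**The case against.** Much of the other side's case stands. Recidivism is a named Aim 1 outcome and comes after Visit 2, so part of the aim is sound. The hypotheses for the Tower Test, delay discounting and stop-signal tasks are worded as associations or group differences, which Visit 2 scores can test. Post-treatment testing also serves the MFP versus TAU comparison. And the pre-treatment BIS-11 is a genuine baseline predictor with its own adherence hypothesis. It is only a partial answer, though: Section 2 says that trait measures "frequently correlate poorly with individual task metrics of impulsivity", and the scale does not measure problem solving or delay discounting.

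Three stronger readings are tempting, and the documents do not support them.

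- *Drop-outs will have no task data.* Section 4a alone could be read so. But Section 3 allows for incompletion, the timeline's Day 29–35 window is not conditional on completing, and the delay-discounting and stop-signal hypotheses concern people who do not adhere. Non-completers are evidently meant to be tested; Section 4a needs aligning.
- *The distortion is large.* If every participant shared the effect, the same simulation gives 16% at 0.5 SD and 34% at 0.8 SD. Section 2 proposes the change for MFP, not for everyone, so these figures do not carry the point.
- *Tasks are given at both visits, so there is no gap.* Section 3 speaks of Veterans who "complete two sessions of questionnaires and neurobehavioral measures". This is best read as a summary of the two sessions together, since Sections 4a, 4b and 7 and the timeline all keep Visit 1 to self-report.

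Nor can the matter be left to a statistical analysis plan, which cannot supply a measurement that was never taken.

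**Conclusion.** For the Day 0–28 outcomes Aim 1 is wrong as written: the tasks follow those outcomes and can show only a retrospective association, in which prior function and treatment received are mixed. This follows from the protocol's own dates and needs no assumption. It does not follow that Aim 1 fails as a whole, because outcomes after Visit 2 can still be predicted and the task hypotheses remain testable as associations.

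The size is uncertain and, on the MFP-only reading, modest: about 7–10% false rejection against a nominal 5%, given 30% drop-out, a 0.5 SD effect and full attendance at Visit 2. All three are assumptions, and at 0.2 SD the excess almost vanishes.

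**What to change.** 1. In Aim 1 and Data Analysis, limit *predictive* for the tasks to outcomes after Visit 2, chiefly treatment re-entry and post-treatment drug and breath tests, with the outcome as dependent variable and the task score as predictor. State that Sections 3 and 4a collect these chart items only where available, so whether a test exists may depend on remaining in or returning to care. Report how many participants have data, and do not count an absent test as negative.
2. Label task associations with Day 0–28 outcomes retrospective. Visit 1 BIS-11 and BAM may be analysed as baseline predictors of those outcomes, as Section 4b hypothesizes, but do not replace the tasks.
3. Align Section 4a with Section 3 so that Visit 2 clearly includes non-completers, and add the Tower Test and the BDI-II to the Day 29–35 measures in the timeline.

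These are wording changes, with no new participants, visits or measures. The price is that in-program prediction by the tasks is given up, and the prediction that remains rests on chart data that may be incomplete.

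Keeping in-program prediction would require the tasks before Day 0. By the protocol's item times, they take 10 + 15 + 12 + 14 = 51 minutes. Visit 1 would become 4 × 10 + 51 = 91 minutes plus consent, against an expected 60–90. Tasks at both visits would total 40 + 30 + 2 × 51 = 172 minutes plus consent, against about 3 hours. Moving them to Visit 1 alone keeps the total at 40 + 30 + 51 = 121 minutes, but removes the post-treatment scores that the MFP versus TAU comparison uses.

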**Visit One:**

The following self-report measures (questionnaires) will be administered with paper-and-pencil:

*Brief Addiction Monitor (BAM)* – The BAM is a 17-item self-report questionnaire that assesses the recent occurrence and frequency of various substances, including marijuana, cocaine, stimulants, and opiates. It additionally has items for the rater to respond to recent health (excellent, very good, good, fair, poor), and recent engagement in risky situations or treatment. Lastly, it has several items asking about symptoms of substance use disorder, such as cravings and difficulties related to substance use (Cacciola et al., 2013). We hypothesize subjects with more reported substance use and less engagement in treatment resources will have poorer treatment adherence. This measure will take approximately 10 minutes to complete.

*Barratt Impulsiveness Scale (BIS-11)* - The BIS-11 is a reliable and valid self-report measure of attentional, motor, and non-planning impulsivity composed of 30 items rated on a 4 point Likert scale from rarely/never to almost always/always (Patton, Stanford, & Barratt, 1995). We hypothesize subjects with higher impulsivity will be more likely to have poorer treatment adherence. This measure will take approximately 10 minutes to complete.

*PTSD Checklist 5* - This is a VA-distributed measure of 20 PTSD-related symptoms (each scored from 0-4) that align with DSM-5 PTSD criteria. It is administered in addition to the SCID itself in order to provide a continuous variable of PTSD symptom severity (Bovin et al., 2016). This measure is being used to account for potential confounding symptomology that may lead to treatment adherence issues. This measure will take approximately 10 minutes to complete.

*Beck Anxiety Inventory* - This is a tally of the subject's self-reported experience of 21 different anxiety-related symptoms in the past week-including the day of testing, where each item is rated on a scale from 0-3 (A. T. Beck, Epstein, Brown, & Steer, 1988). This measure is being used to

account for potential confounding symptomology that may lead to treatment adherence issues. This measure will take approximately 10 minutes to complete.

Visit Two:

The following self-report measures (questionnaires) will be administered with paper-and-pencil:

*Barratt Impulsiveness Scale (BIS-11)* – See above for description

*Quality of Life Inventory (QOLI)* – The QOLI assesses the importance of 16 life domains on a 3-point rating scale, as well as current satisfaction of each domain (6-point scale). The scores are summed to determine quality of life. This is a quick self-report questionnaire that has been normed in a community sample of adults. Higher scores indicate better quality of life. We hypothesize that those with better treatment adherence and less evident impulsivity on neurobehavioral measures will indicate better quality of life (Frisch, Cornell, Villaneuva, & Retzlaff, 1992). This measure takes approximately 10 minutes to complete.

*Beck Depression Inventory-II (BDI-II)* - The BDI-II is a 21-question, multiple-choice self-report questionnaire that is widely used in clinical and research practice for the purposes of measuring reported symptoms of depression. This has been widely established as a reliable and valid measure (Aaron T. Beck, Steer, & Brown, 1996). This measure takes approximately 10 minutes to complete.

The following tasks will be completed via administration by research staff:

*Delis-Kaplan Executive Function System (DKEFS) Tower Test* – The DKEFS Tower Test is a neuropsychological measure examining the executive functioning ability, specifically the ability to plan and sequence behavior. The test consists of two boards with pegs and several beads with different shapes. The test requires the individual to complete a timed-task requiring planning and sequencing in order to move the pegs in an instructed manner. We hypothesize errors on the Tower Test will be significant associated with poorer performance on neurobehavioral measures (as evident by more errors and faster reaction times) and with poorer treatment adherence. Time and errors are considered for scoring. The task requires approximately 10 minutes to complete.

The following laboratory performance measures will be conducted on a desktop computer:

*Adjusting Delay Discounting (DD) Task* - This decision task assesses how a subject de-values a hypothetical money reward the longer he or she would have to wait to receive it (“delay-discounting”). The participant chooses between immediate adjusting rewards (e.g., “\$5 now”), and delayed rewards (e.g., “\$10 in 1 week”). Participants are exposed to a series of choices where the future reward magnitudes are \$10, \$25, \$100, \$250, \$1000 or \$2500 (for delayed rewards) at delay periods of 1 day, 1 week, 1 month, 6 months, 1 year, 5 years or 25 years. The computer program varies the choices available across trials according to an algorithm that rapidly converges on an indifference point for each delay interval for every reward amount. These indifference points enable calculation of a single constant (“K”) that characterizes the severity of DD for that subject. The task ends once indifference points have been determined for each magnitude at each delay, usually within four minutes. Two different question series will be administered, one series involving smaller dollar amounts (per above), and another series involving much higher amounts (e.g. \$50,000) in order to assess individual differences in the reduction of delay-discounting severity typically observed when subjects consider very high hypothetical reward magnitudes. We hypothesize that subjects who do not adhere to treatment will devalue delayed rewards more severely, and will not show as great a reduction in discounting

when very large hypothetical rewards are presented. This task requires approximately 15 minutes.

**Stop-Signal Task (SST)** - In this rapid-response impulsivity task, participants view a series of go stimuli ("X" or "O") in the center of the screen and are told to press the keyboard left arrow button when they saw an "X" and to press the right arrow button when they see an "O". On a subset of trials, a stop-signal (a 500 Hz tone presented for 250ms) is presented as a short delay after the go stimulus. Participants are instructed to respond as quickly and accurately as possible, but to withhold their response on Stop trials (on trials with the tone). The delay of the onset of the stop-signal is dynamically titrated by 50 ms intervals to promote a 50% rate of successful stops. The Stop Signal Reaction Time (SSRT) will be calculated as the interval between "go" and subsequent "stop" signals at which the subject can stop half the time. We hypothesize that subjects who do not adhere to treatment will show a faster SSRT, meaning that their response style is more "ballistic," and difficult to stop once-launched. This task requires approximately 12 minutes.

**The Emotional Go-NoGo Task** – This task presents a series of facial stimuli with either no facial expression, or with expression of an emotion, for 500 ms each, atop a black screen. A white fixation crosshair is displayed between Face stimuli. Facial stimuli are composed of sets of multiple faces of each of several actors/models, across neutral and different emotions. The subject is to respond with a keyboard or mouse press when he or she sees either a neutral face (neutral blocks) or an emotional face (emotion blocks). Blocks of trials are set in pairs, where at the start of one block, subjects are instructed on-screen that the emotional face is the target (to which to respond) and the neutral face is the non-target, and at the start of the counterpart block, the reverse instruction holds true in the other block. Attentional capture by either positive or negative emotions will be indexed by the rate of commission errors to emotion non-target faces relative to commission errors to neutral non-target faces. The task lasts roughly 14 minutes, including self-paced rest breaks between blocks.

Project timeline (Day 0 is the first day of IOP)		
Timeline	Study activities	Measures
Day -7 – Day -1	
 
- Contact with potential subjects for recruitment during a face to face meeting when they are in the SATP clinic
 
- Consent and pre-treatment baseline assessment
 
	Brief Addiction Monitor (BAM), Barrett Impulsivity Scale-11 (BIS-11), Posttraumatic Checklist-5 (PCL-5), Beck's Anxiety Inventory
Day 0 – Day 28	
 
- Participants engage in either MFP or TAU treatment during their IOP engagement
 
	N/A
Day 29 – Day 35	
 
- Post-treatment assessment
 
- Chart review: treatment engagement (appointment no shows, early drop out) and Breathalyzer/UDS results, results of Beck Depression Inventory and Quality of Life Inventory.
 
	BIS-11, Delay Discounting Task, Stop-Signal Task, Emotional Go-NoGo task, Quality of Life Inventory
Day 120	
 
- Chart Review: recidivism (treatment re-entry) and Breathalyzer/UDS results
 
	N/A

